3.3. Exploratory Objectives

The exploratory objectives are to develop novel approaches for the characterization and measurement of immune modulation and tissue repair using biomarkers that could enable correlation of in vitro, nonclinical and clinical function of PDA-002.

4. INVESTIGATIONAL PLAN

4.1. Overall Study Design and Plan

This is a Phase 1, multicenter, open-label, dose-escalation study in subjects with PAD and DFU. The study will enroll up to 24 subjects. The study will utilize a “3 + 3” dose escalation design with

3 to 6 subjects enrolled into each of 4 dose cohorts. Subjects will be assigned to a dose cohort based on the order of entry into the study.

Four PDA-002 dose cohorts are planned in this study:

Cohort 1: 3×10^6 cells administered on Study Days 1 and 8.

Cohort 2: 10×10^6 cells administered on Study Days 1 and 8.

Cohort 3: 30×10^6 cells administered on Study Days 1 and 8.

Cohort 4: 100×10^6 cells administered on Study Days 1 and 8.

Initially, 3 subjects will begin dosing at the 3×10^6 cells dose level.

All subjects in a given dosing-cohort must complete 14 days of follow-up and the data reviewed by an internal Data Monitoring Committee (DMC), and approval given to dose escalate before accrual to the next dosing cohort can begin.

Subjects who discontinue from the study prior to the Study Day 15 assessments for reasons other than a dose-limiting toxicity (DLT) will be replaced. Subjects who experience a DLT should continue to complete all protocol assessments and will not be replaced.

This pattern of enrollment will continue until the MTD is determined or the highest planned dose level is tested. Six subjects must be treated at a given dose level before the MTD can be declared. The MTD is defined as the highest PDA-002 dose level for which the incidence of DLT is ≤ 1 out of 6 subjects. At any dose level, if 2 or more subjects experience a DLT within 14 days of dosing, that cohort will have exceeded the MTD. If a previous dose level was well tolerated and

no subjects experienced DLT at that level, an intermediate dose level may be defined by protocol amendment.

Subjects will undergo screening evaluations to determine eligibility within 28 days of Study Day 1. Following Screening, subjects will be assigned to the appropriate cohort as outlined above and will receive IP. In the case of bilateral limb ulcers, the treated limb will be the limb that has the largest ulcer total surface area. During the treatment period, subjects will receive intramuscular (IM) injections of PDA-002 on Study Days 1 and 8. No more than 1 subject may begin treatment in any 48-hour period. During the follow-up period subjects will be evaluated on Study Days 15 and 29, and Months 3, 6, 9, 12, and 24. All subjects are to receive standard of care treatment in addition to IP. An interim analysis will be performed after the last subject completes 3 months of follow-up.

All subjects who receive any dose of PDA-002 will participate in the 24-month follow-up period.

4.2. Study Endpoints

4.2.1. Primary Efficacy Endpoint

The primary endpoint is determination of the MTD defined as the highest PDA-002 dose level for which the incidence of DLT is ≤ 1 out of 6 subjects.

4.2.2. Secondary Efficacy Endpoints

The secondary endpoints are to explore clinical efficacy and include:

- 1) ABI and TBI will be calculated by dividing the systolic blood pressure at the ankle or toe by the systolic blood pressures (Doppler technique) in the arm. ABI and TBI will be measured during Screening, on Study Days 1 and 8 prior to administration of IP and on Study Days 15 and 29 and Months 3, 6, 9, 12 and 24.

- 2) The number of ulcers and the size of the index ulcer (length, width, depth and EZ Graph area) will be evaluated and photographs of ulcers taken during Screening and again on Study Days 1, 8, 15, and 29 and Months 3, 6, 9, 12, and 24 (Appendix E, Appendix F of study protocol).
- 3) Time to major amputation (above the ankle) of treated leg, doubling of index ulcer total surface area from baseline, de novo gangrene of treated leg, reopening of closed ulcer, index ulcer reduction by 50%, and time to ulcer healing. Number of ulcers that completely close at 3 months, if they closed at least 50% at one month.
- 4) Extent of ulcers will be examined with the Wagner Grading Scale. The Wagner Grading Scale (Section 16.3) is assessed during Screening and on Study Days 1, 8, 15, and 29 and Months 3, 6, 9, 12, and 24.
- 5) Rutherford Criteria (Section 16.4) assessed during Screening and on Study Days 1, 8, 15, and 29 and Months 3, 6, 9, 12, and 24.
- 6) Leg rest pain score - visual analogue scale (VAS) (Appendix D of study protocol) graded from 0 (pain free) to Grade 10 (maximum pain) during Screening, on Study Days 1 and 8 prior to administration of PDA-002 and on Study Days 15 and 29 and Months 3, 6, 9, 12, and 24.
- 7) Overall survival at 24 months (time from PDA-002 administration to any cause of death, subjects still alive will be censored at the date of last follow-up).
- 8) Incidence of hospitalization (all cause).

4.2.3. Exploratory Efficacy Endpoints

Serum samples and peripheral blood mononuclear cells (PBMC) may be collected at Screening and Study Days 1, 8, 15, and 29, and Months 3 and 6 for the development of potential new biomarkers predictive of efficacy as well as for the characterization of the DFU population.

Polymerase chain reaction (PCR)-based evaluation of levels of messenger ribonucleic acid (mRNA), as well as proteomics-based assessment of protein levels in response to treatment will

be the exploratory endpoints in this study. This exploratory efficacy endpoint will be analyzed by the sponsor and will be presented in another document.

4.2.4. Safety Endpoints

The following safety assessments will be performed:

- 1) AEs including DLTs and serious adverse events (SAEs).
- 2) Vital signs, height and weight, and physical examinations.
- 3) Laboratory tests.
 - a. Serum chemistry, lipid profile, fatty acids, hematology, urinalysis and pregnancy
 - b. Coagulation tests
 - Prothrombin time (PT), partial thromboplastin time (PTT), and thrombin activation time (TAT)
 - D-dimers
 - Fibrinogen
 - Tissue factor procoagulant activity (TF-PCA)
 - Platelets
 - c. Immunologic/Inflammation Assessments
 - Anti-HLA antibodies
 - C-reactive protein
 - Quantitative assessment of serum immunoglobulins (IgA, IgM, and IgG)
 - Vascular endothelial growth factor (VEGF)
 - Cytokines: interleukin (IL)-1 β , tumor necrosis factor (TNF- α), IL-6, IL-8, IL-10, and transforming growth factor- β (TGF- β)
 - d. Tryptase and Histamine
 - e. Troponin I
 - f. Hemoglobin A1c
 - g. Circulating endothelial cells (CECs)

- 4) Assessment of injection sites.
- 5) Electrocardiograms (ECGs).
- 6) Retinal examinations.
- 7) Magnetic resonance imaging (MRI) or computed tomography (CT) of the chest, abdomen, and pelvis.
- 8) Concomitant medications and procedures.

4.3. Stratification , Randomization and Blinding

This is an open-label study. Eligible subjects will be assigned to a cohort based on the order in which they enter the study according to the dose escalation scheme.

4.4. Sample Size Determination

Based on the “3 + 3” dose escalation design, each cohort will enroll 3 to 6 subjects and the study will enroll up to a total of 24 subjects. This sample size is not determined based on formal statistical calculations, but on clinical considerations.

5. GENERAL STATISTICAL CONSIDERATIONS

5.1. Reporting Conventions

- I** [REDACTED]
[REDACTED]
[REDACTED]
- I** [REDACTED]
[REDACTED]
- I** [REDACTED]
[REDACTED]
- I** [REDACTED]
[REDACTED]
[REDACTED]
- I** [REDACTED]
[REDACTED]
- I** [REDACTED]
[REDACTED]

5.2. Analysis Populations

5.2.1. Efficacy Evaluable Population

The Efficacy Evaluable (EE) Population includes all subjects who received any amount of IP, and have a baseline and at least one post-baseline efficacy assessment.

5.2.2. Safety Population

The Safety population includes all subjects who received any amount of IP.

6. SUBJECT DISPOSITION

Total number of subjects with screen failures will be summarized.

Subject disposition (number of subjects entered, discontinued, primary reason for discontinuation) by cohort will be summarized using frequency and percent for all enrolled patients.

A summary of subjects enrolled by site will be provided.

7. PROTOCOL DEVIATIONS/VIOLATIONS

The protocol deviations/violations were identified and assessed by clinical research physician or designee. The protocol deviations/violations will be summarized by cohort for the EE population.

A by-subject listing of subjects with protocol violations in the Safety population will be provided.

8. DEMOGRAPHICS AND BASELINE CHARACTERISTICS

Summaries for the demographics and baseline characteristics will be summarized for the EE population. Individual subject listings will be provided to support the tables.

8.1. Demographics

Baseline and demographic characteristic will be summarized by cohort for the EE population.

Age (years), height (cm), weight (kg), and BMI (weight (kg)/ height (m²)) will be summarized using descriptive statistics for the following: Age category (<65 versus \geq 65 and < 75 versus \geq 75 years), sex, race, and ethnicity.

Age will be calculated as follows: age = Integer \leq [(Date of enrollment – Date of Birth + 1) / 365.25].

8.2. Baseline Characteristics

Ulcer assessment (efficacy endpoints) will be summarized descriptively at Baseline by cohort. In addition, the baseline values for all laboratory parameters from the central laboratory will be summarized descriptively by cohort.

8.3. Medical History

A summary of medical and surgical history will be presented by system organ class and preferred term using MedDRA version 17.0. A similar summary will be generated for the currently active abnormalities only, per body system.

8.4. Prior and Concomitant Medications

Medications that started before the start of study treatment and continued after the start of study treatment will be counted as both prior and concomitant medications.

8.4.1. Prior Medications

Prior medications are defined as medications that started before the start of the study treatment and, either ended before the start of the study treatment, or continued after study treatment. A summary will be presented showing the number and percentage of subjects who took prior medications by WHO therapeutic drug class and generic drug name, as coded by WHO dictionary 01Mar2014.

8.4.2. Concomitant Medications

Concomitant medications are defined as the medication that was either initiated before the first dose of study drug and continued during the study treatment, or initiated on/after the date of the first dose of study drug and on/before the date of treatment discontinuation.

A summary will be presented showing the number and percentage of subjects who took concomitant medications by WHO therapeutic drug class and generic drug name, as coded by WHO dictionary 01Mar2014.

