### **4.3. Study Duration**

[figure not shown]
The study consists of a 0 to 28 day screening/baseline period followed by a 7-day treatment period (treatment on Study Days 1 and 8) plus a 24-month follow-up period.

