## 6. PROCEDURES

The study is divided into 3 periods: Screening/baseline, Treatment and Follow-up with associated evaluations and procedures that must be performed at specific timepoints. The Screening/Baseline Period is defined as the 28 days before administration of IP, during which subjects are evaluated for eligibility. The Treatment Period consists of Study Days 1 and 8 when the IP is administered. The Follow-up Period begins after Study Day 8 and is completed at Month 24. An interim analysis of safety and efficacy will be performed after the last subject in the study completes 3 months of follow-up. All subjects should be followed for the full 24 months regardless of clinical response.

All subjects are to receive standard of care for DFU in addition to IP.

The schedule of study procedures is shown in the Table of Events ([Table 2](#)) and the Study Design Schema ([Figure 2](#)). A description of specific study procedures is provided in the following subsections.

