## **9. CONCOMITANT MEDICATIONS AND PROCEDURES**

All medications (prescription and non-prescription), treatments and therapies taken from 30 days prior to Visit 1 (the Screening/Baseline Visit) until Month 24 must be recorded on the appropriate page of the eCRF.

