### **10.7. Safety Analysis**

The Safety analyses will be conducted using the Safety Population as defined in Section 10.2. Adverse events, vital sign measurements, physical examination findings, clinical laboratory test results, injection site assessments, MRI/CT scan results, retinal examination results, ECG interpretations, concomitant medications and procedures will be tabulated and summarized by cohort, as appropriate.

Adverse events observed will be classified using the Medical dictionary for Regulatory activities (MedDRA) classification system. The severity of the toxicities will be graded according to the National Cancer Institute (NCI) Common Terminology Criteria for Adverse Events (CTCAE) v 4.03 whenever possible.

[http://ctep.cancer.gov/protocolDevelopment/electronic\\_applications/ctc.htm#ctc\\_40](http://ctep.cancer.gov/protocolDevelopment/electronic_applications/ctc.htm#ctc_40)

The frequency of adverse events will be tabulated by MedDRA System Organ Class and Preferred Term. In the by-subject analysis, a subject having the same event more than once will be counted only once. Adverse events will be summarized by NCI CTCAE grade. Adverse events leading to discontinuation from treatment, events classified as NCI CTCAE Grade 3 or higher, study-drug-related events, and serious adverse events will be tabulated and listed separately. By-subject listings of all adverse events, serious adverse events, discontinuations due to AEs, and deaths will be provided.

Clinical laboratory data will be summarized. Laboratory data will be graded according to NCI CTCAE version 4.03 criteria wherever possible. The frequencies of the worst severity grade observed during treatment will be displayed in cross-tabulations by screening status.

Vital signs, ECG, retinal examination and MRI/CT scan data will be summarized by cross-tabulations presenting normal and abnormal values.

Graphical displays will be provided where useful in the interpretation of results.

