9.1. Treatment Duration

Treatment duration in days (calculated as last dose date – first dose date + 1) will be summarized by cohort using the Safety population.

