11.3. Clinical Laboratory Evaluations

The change from baseline in the following laboratory parameters will also be summarized descriptively over time, by cohort and visit:

- a. Serum chemistry, lipid profile, fatty acids, hematology, urinalysis and pregnancy
- b. Coagulation tests
 - Prothrombin time (PT), partial thromboplastin time (PTT), and thrombin activation time (TAT)
 - D-dimers
 - Fibrinogen
 - Tissue factor procoagulant activity (TF-PCA)
 - Platelets
- c. Immunologic/Inflammation Assessments
 - Anti-HLA antibodies
 - C-reactive protein
 - Quantitative assessment of serum immunoglobulins (IgA, IgM, and IgG)
 - Vascular endothelial growth factor (VEGF)
 - Cytokines: interleukin (IL)-1 β , tumor necrosis factor (TNF- α), IL-6, IL-8, IL-10, and transforming growth factor- β (TGF- β)
- d. Tryptase and Histamine
- e. Troponin I
- f. Hemoglobin A1c
- g. Circulating endothelial cells (CECs)

Spaghetti plots of individual lab values and change from baseline values over time will be provided for these lab parameters.

By-subject listings will also be provided for the laboratory data.

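### SAP 8.4.2 closes the window for new concomitant medications at treatment discontinuation (by inference Day 8), so drugs started in about 99% of the time to Month 24 reach no medication table; a procedures summary and the graded laboratory table are also absent

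*SAP*

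**What the plan says.** **Medications.** SAP 8.4.1 defines prior medications as those started before study treatment, whether or not they continued. SAP 8.4.2 defines concomitant medications as those started before first dose and continued during treatment, or those "initiated on/after the date of the first dose of study drug and on/before the date of treatment discontinuation". Protocol 9 requires that medications, treatments and therapies from 30 days before Visit 1 "until Month 24 must be recorded on the appropriate page of the eCRF". Protocol 6.4.5 sets the same end for collecting concomitant medication use.

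**Treatment period.** Protocol 6: "The Treatment Period consists of Study Days 1 and 8 when the IP is administered", and "The Follow-up Period begins after Study Day 8 and is completed at Month 24". Protocol 4.3 describes a "7-day treatment period (treatment on Study Days 1 and 8) plus a 24-month follow-up period". SAP 9.1 gives "Treatment duration in days (calculated as last dose date – first dose date + 1".

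**Procedures.** Protocol 10.7 promises tabulation by cohort of concomitant medications and procedures, as appropriate, with no Day 8 limit. SAP 4.2.4 lists concomitant procedures among the safety endpoints, and SAP 16.2.3 imputes their partial start dates. No SAP section summarizes them.

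**Laboratory data.** Protocol 10.7 grades laboratory values by CTCAE v4.03 and adds: "The frequencies of the worst severity grade observed during treatment will be displayed in cross-tabulations by screening status". SAP 11.3 says instead: "The change from baseline in the following laboratory parameters will also be summarized descriptively over time, by cohort and visit", with individual-value plots and listings. It contains no grading.

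**Declared changes.** SAP Section 14 covers the restriction of gangrene and ulcer doubling to the treated leg, the added time-to-event analyses, and the dropping of urinary cotinine. It mentions neither a narrower medication window nor the two missing summaries.

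**The concern.** Treatment lasts about a week and follow-up lasts two years. A definition tied to the end of treatment suits a drug given continuously; here it closes almost at once.

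What may happen later matters to the reading of the results. Protocol 9.2 prohibits no medication except investigational agents. Protocol 9.1 asks only for an effort to hold standard care stable for the first 12 weeks. Inclusion criterion 7 rules out planned revascularization for only 3 months after Screening, and Protocol 4.2 allows debridement. Yet ulcer size, healing, ABI/TBI, amputation and survival are described to Month 24, in uncontrolled cohorts of 3 to 6 subjects. A new antibiotic, anticoagulant or wound therapy, or a revascularization, is a plausible alternative explanation for a change in any of these. The planned summaries would not show it if it began after Day 8.

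The laboratory omission is secondary. The protocol promised a table of graded shifts, the SAP does not deliver it, and the protocol's own version is confined to the treatment period.

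**Working it through.** No power or sample-size calculation applies. The check is date arithmetic and a comparison of definitions.

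**1. Reproduce the plan's figure.** Doses fall on Days 1 and 8. Elapsed time is 8 − 1 = 7 days, which matches Protocol 4.3. By the SAP 9.1 formula, treatment duration is 8 − 1 + 1 = 8 days.

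**2. Classify a drug first started on Day 9**, taking treatment discontinuation as the last dose date:
- Prior (SAP 8.4.1) needs a start before study treatment: no.
- Concomitant, first limb (SAP 8.4.2), needs a start before first dose: no.
- Concomitant, second limb, needs a start on or before Day 8: no.

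It belongs to neither category and so to neither table.

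**3. Size of the excluded window.** Share excluded = (T − 8)/T, where T is the number of days from first dose to Month 24.
- 24 months counted from Day 1, T = 730 (assumed as 2 × 365): 722/730 = 98.9%.
- 24 months counted from Day 8, T = 8 + 730 = 738: 730/738 = 98.9%.
- 28-day months, T = 24 × 28 = 672: 664/672 = 98.8%.
- A subject given only the Day 1 dose: 729/730 = 99.9%.

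The window therefore covers 8/730 = 1.1% of the time since first dose. Because Protocol 6 starts the Follow-up Period after Day 8, 100% of that period lies outside. A window ending at the Month 3 interim (91 days) would cover 91/730 = 12.5%; one ending at Month 24 would cover all of it.

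**4. The protocol's laboratory table.** Eight visits are scheduled after Day 1: Days 8, 15 and 29 and Months 3, 6, 9, 12 and 24. If the treatment period means Days 1 to 8, only Day 8 falls inside, and 7/8 = 87.5% of these visits fall outside. Protocol 6.2 has chemistry and hematology drawn before dosing on each treatment day. For those panels the table would hold no value taken after the second dose, although Protocol 6.4.5 measures them at every visit.

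**5. Protocol promise against SAP delivery.**
- Medications: collected to Month 24 and to be tabulated; the SAP table closes to new starts at treatment discontinuation; not declared in Section 14.
- Procedures: to be tabulated as appropriate; no SAP summary; not declared.
- Laboratory grades: worst grade by screening status; absent from SAP 11.3; not declared.

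**The case against.** **Day 8 is an inference.** No readable text defines the date of treatment discontinuation. Protocol 8.2.1 and 12 treat stopping the product and leaving the study together, and SAP 5.1 and 16.1, where a definition might sit, are redacted. This stands as a caveat. Day 8 is, however, the only dated end of treatment in the documents, and if end of study was meant, the SAP still needs to say so. The protocol's reference to grades during treatment is likewise undefined there, and a looser on-study reading is possible.

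**The 99% is calendar time, not medications.** This stands. A reader might infer that nearly all medication use is lost. The documents do not support that: therapy ongoing at first dose and continued is counted, Protocol 9.1 encourages stable care for 12 weeks, and nothing indicates how many new starts to expect.

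**Laboratory toxicity is covered elsewhere.** This largely stands. A reader might infer that delayed laboratory toxicity would appear in no graded summary. That is wrong. Protocol 11.3 makes a laboratory abnormality an adverse event if it is clinically important, needs treatment or leads to discontinuation. Adverse events are recorded to 24 months after the last dose, and SAP 11 summarizes them by CTCAE grade, with Grade 3 or higher tabulated separately. Nor would one subject's large shift vanish into a cohort mean, since SAP 11.3 provides individual plots and listings. What is missing is the laboratory-grade summary itself, including abnormalities that do not qualify as adverse events.

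**Partial coverage and limited stakes.** Major amputation and hospitalization have their own analyses. SAP Section 8 promises listings to support its tables, though none is named for medications started after Day 8. Efficacy is descriptive, and the primary endpoint is the MTD from DLTs. A reader might conclude that the Month 24 results cannot be interpreted; that goes too far, because the subject-level data are collected. These points lower the severity but do not close the gap.

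**Conclusion.** The point holds as a reporting gap that should be fixed before the SAP is finalized. As SAP 8.4.2 is most naturally read, medications first started in about 99% of the time from first dose to Month 24 (722 of 730 days) appear in no SAP medication table, although the protocol collects them and promises their tabulation. Concomitant procedures have no summary, and the worst-grade laboratory cross-tabulation is dropped; Section 14 declares neither omission.

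The percentage assumes that treatment discontinuation means the last dose date, that both doses are given, and that 24 months is about 730 days. The sensitivity range is 98.8% to 99.9%. The laboratory loss is confined to laboratory-grade summaries, and determination of the MTD is not affected.

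**What to change.** 1. **SAP 8.4.2:** define concomitant as any medication taken on or after first dose through Month 24 or last contact. Drop the reference to treatment discontinuation. Splitting the table by period is optional.
2. **Procedures:** add a table by cohort over the same window, with revascularization and debridement of the treated leg shown separately.
3. **SAP 11.3:** restore the CTCAE v4.03 table of baseline grade by worst grade, using all values after first dose through each panel's last scheduled visit. Chemistry, hematology and urinalysis run to Month 24; several other panels stop at Day 15, Day 29, Month 3 or Month 6.
4. **Protocol 10.7:** align the during-treatment wording with that window.
5. **SAP Section 14:** list any of these summaries that the sponsor decides not to produce.

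The cost is SAP wording, one phrase in the protocol and a few more tables, all on data already collected. No visit, dose or design feature changes.
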